Official Title: Improving Detection and Evidence-based Care of NAFLD in Latinx and Black Patients With Type 2 Diabetes (NAFLD-DM): A Pilot Study

NCT: NCT05844137

IRB Document Date: 5/31/2024

Improving detection and evidence-based care of NAFLD in Latinx and Black patients with type 2 diabetes (NAFLD-DM): A pilot study

PI: [name]

Page 1 of 7

Version 2: May 31, 2024

Background: NAFLD is a critically overlooked T2D complication, and T2D accelerates NAFLD progression to poor outcomes, such as cirrhosis, liver cancer and death.^{1, 2} As with other T2D complications, **racial and ethnic disparities exist in detection and care of NAFLD**, although the drivers of these disparities are poorly understood, especially in the context of T2D care.³ Based on my prior work published in *Hepatology*,⁴ there are racial/ethnic disparities in who receives liver biopsy to diagnose NAFLD. For instance, of the 350 patients with T2D who underwent liver biopsy for NAFLD between 2007-2019 in DUHS, only 1.7% and 13% of patients were Latinx and Black, respectively.⁴ This is striking when considering that these underrepresented minority groups are disproportionately impacted by T2D complications and poor liver outcomes due to NAFLD.³ **Because T2D imparts higher risk of poor liver outcomes due to NAFLD,^{1, 2} and because underrepresented minority groups are likewise at higher risk of these outcomes, Latinx and Black patients with T2D should be prioritized for proactive detection and intensive management of NAFLD.^{5, 6}**

Diabetes care guidelines specifically call for further evaluation of NAFLD in T2D in the presence of abnormal liver enzymes, or when imaging has revealed hepatic steatosis.⁶ Detection of high-risk forms of NAFLD is critical in T2D, not only because of the elevated risk of poor NAFLD outcomes in T2D, but also because we can use T2D approaches to effectively treat NAFLD.^{5, 7, 8} In a recently published study,⁹ we showed that T2D medications that prevent NAFLD progression are vastly underutilized in high-risk patients with T2D. Currently, **disparities in the detection and treatment of NAFLD in patients with T2D are poorly characterized; however, given known racial and ethnic disparities in biopsy rates and NAFLD outcomes, we urgently need to understand disparities in NAFLD detection and care in T2D.** Such data could directly inform the **development of interventions to foster the equitable management of T2D and NAFLD.** To address these critical issues, I propose a KL2 program of research that will characterize health disparities in NAFLD detection and care in T2D, and then develop and pilot a culturally-competent intervention that will improve recognition and management of Latinx and Black patients with T2D and NAFLD.

Significance: NAFLD-related liver disease and mortality are high – based on 2015 data, 16.5 million Americans have NASH (i.e., high-risk NAFLD) and mortality in patients with NAFLD is up to 1.27 million annually.¹⁰ These rates are projected to increase by over 130% in the next 10 years.¹⁰ This increased clinical burden will result in direct medical and societal costs of over \$300 billion/year.^{11, 12} Efforts to prevent this rise in NAFLD complications and costs should focus on populations at highest risk for poor outcomes; thus, this proposal's focus on T2D and high-risk racial/ethnic groups is highly significant. Furthermore, given known health disparities in NAFLD detection, and in T2D care in general, our emphasis on addressing disparities is crucial. This proposal will generate a patient-facing intervention that will improve evidence-based care of NAFLD in T2D, with a focus on reaching Latinx and Black patients who are disproportionately impacted by T2D complications,¹³ especially NAFLD.³ **This work is critically urgent** as the U.S. burden of NAFLD is rising, and several drugs for NAFLD in T2D will come to market soon; this proposal will support equitable use of current and emerging therapies for NAFLD, assuring that those with the greatest need are able to access effective treatment. Because current services are already struggling to reach rising numbers of patients with NAFLD, a major strength of this proposal is its support of **multidisciplinary efforts** to tackle this public health threat.

Innovation: This proposal is novel in multiple ways. First, the drivers underlying health disparities in NAFLD detection are poorly understood, and this proposal will address this gap. Second, there are no existing interventions to promote detection and management of NAFLD as part of T2D care, and certainly none to address disparities in these areas. Third, I am proposing an innovative intervention development approach that will leverage community engagement resources at Duke and maximize intervention relevance and feasibility through use of stakeholder input. No studies have queried minority communities to understand how best to design/deliver an intervention to improve outcomes in NAFLD and T2D. Notably, this proposal will proactively improve the care of an exceedingly high-risk, high-cost group through a joint **T2D/NAFLD intervention.** To our knowledge, this will be the first intervention geared towards intensively co-managing these linked conditions.

Research Strategy/Approach

This project will assess the feasibility and acceptability of an intervention for improved detection and evidence-based care of NAFLD in Latinx and Black patients with T2D.

Improving detection and evidence-based care of NAFLD in Latinx and Black patients with type 2 diabetes (NAFLD-DM): A pilot study

[figure not shown]
PI: [name]

Page 2 of 7

Version 2: May 31, 2024

Rationale: Below is a conceptual framework that has guided the design, and will inform the execution, of our intervention. This framework includes features of the Health Belief Model (HBM)¹⁴ to highlight patient-level strategies for disease prevention, and the Chronic Care Model (CCM)¹⁵ to highlight the system-level components aimed at improving the care of NAFLD. As depicted in the Figure below, this intervention represents an innovative approach to **redesigning care** and using available **EHR** to promote equitable detection of NAFLD (right side of figure). Once detected, we will engage patients with NAFLD and T2D in strategies to promote their overall health and halt, or even reverse their NAFLD. These patient-level approaches will consider how to alter patient perceptions (i.e., **perceived threat** of NAFLD, **perceived benefits & barriers**) and understand patient **cues to action**, to promote patient engagement with the care plan (left side of Figure). The ultimate objective of this project is to lead to **productive interactions** between patients and the care teams (center of Figure) that will ultimately lead to better detection and care of NAFLD in those at highest risk. Prior work has helped us develop this intervention in a culturally-appropriate manner to allow us to reach high-risk racial/ethnic groups with T2D and NAFLD. This will be a feasibility pilot.

Figure: Conceptual framework guiding intervention design and execution

Improving detection and evidence-based care of NAFLD in Latinx and Black patients with type 2 diabetes (NAFLD-DM): A pilot study

PI: [name]

Version 2: May 31, 2024

Intervention content and design: The first intervention component will involve proactive detection of NAFLD in Latinx/Black patients with T2D using DEDUCE; this EHR-based approach will allow us to identify eligible study participants in DUHS based on our inclusion/exclusion criteria listed below. The next intervention component will focus on delivery of evidence-based care, which will rely on a proactive care team that is knowledgeable about NAFLD and can intervene, as well as an informed and activated patient who wants to engage with care.

Once identified, patients will receive the following guideline-concordant content as part of the intervention: a) diet/lifestyle support, with counseling on hypocaloric diet and moderate-intensity exercise;⁵ b) NAFLD education;⁵ c) medication management, with proactive use of T2D medications known to be protective against NAFLD progression (pioglitazone, GLP-1RA, SGLT2i);^{5, 7, 16} and d) clinically-indicated liver testing and care based on guidelines.⁵ The content of this intervention will be delivered remotely via telehealth approaches. In order to ensure feasibility within the proposed KL2 timeline, we have limited the pilot duration to 3 months. This will allow time to observe change in liver enzymes, as well as HbA1c. Table 1

shows when intervention content will be delivered throughout the

Study population: We will enroll 10-15 Latinx/Hispanic and 10-15 Black patients with T2D and NAFLD, based on elevated ALT and exclusion of other liver diseases (e.g., viral hepatitis, alcohol abuse).

Research activity:

Detection of NAFLD in T2D: The Duke DEDUCE tool will be used to generate a report of potentially eligible Latinx and Black patients with an ICD code for T2D (E11.xx) and at least one ALT >40 IU/mL in males or > 31 IU/mL in females¹⁷ in the preceding 12 months. For this feasibility pilot, we will also restrict eligibility to patients who have a PCP or Endocrinologist in DUHS to facilitate communication regarding T2D medication changes during the study period. We anticipate >2,000 patient will meet our inclusion and exclusion criteria. A report will be exported from DEDUCE and I will review the charts of potentially eligible patients to exclude individuals with liver dysfunction likely due to an etiology other than NAFLD. We will not exclude patients with an ICD-10 code for NASH (K75.81), as long as they are not medically optimized (i.e. on pioglitazone and GLP-1RA), since these individuals serve to benefit from the intervention.

The first 50 patients who meet eligibility will be mailed a letter or sent a MyChart message with opt-out instructions. Patients who do not opt out will be contacted by phone and, if interested, they will sign an e-

consent form via REDCap. In parallel to the above recruitment approach, we will also advertise this study in the community with the help of community partners that had assisted us in the design of the intervention, i.e., Latin-19 group and the AME Zion partnership. An IRB-approved flyer (with brief inclusion/exclusion criteria) will be created and placed in community spaces with the help of our community partners. Community members who are interested in the study, and who

Table 1: NAFLD-DM study visits and timing	Months			
	0	1	2	3
Enrollment, consent review (~20 min, remote visit)	x			
Surveys (~20-30 min, online or on phone)	x			x
NAFLD education (~30 min, remotely)	x			
Diet and lifestyle support (~30 min each, remotely)	x	x	x	
Medication changes (~20 min, remotely) *	o	o	o	o
If indicated, ordering tests and referrals *	o	o	o	o
Interviews (~30 min, remotely)				x

*Timing of med changes and ordering of tests/referrals will vary by participant.
x Visits that will occur for all participants.
o Visits that may or may not occur and are dependent upon individual needs.

are also part of DUHS, will be provided with a study contact number to let us know of their interest. We will use the EHR to determine their eligibility, and if eligible, consent will be obtained as above.

Baseline surveys will be conducted by phone or completed online via Duke REDCap. For participants completing surveys by phone, we will ensure that a copy of the survey is mailed or emailed in advance, in case participants prefer to review content in advance. We will survey: self-efficacy,¹⁸ and quality of life surveys¹⁹). The most recent BMI in the EHR will be used for the purpose of characterizing the participant population – if there is no BMI documented within 1 year of enrollment, we will count BMI data as missing. For HbA1c, if there is no documented HbA1c within 3 months of enrollment to the study, or ALT and ALT within 6 months of enrollment, we will order these tests to be completed at baseline.

Improving detection and evidence-based care of NAFLD in Latinx and Black patients with type 2 diabetes (NAFLD-DM): A pilot study

PI: [name]

Page 4 of 7

Version 2: May 31, 2024

Evidence-based care of NAFLD in T2D: Intervention content will include: 1) NAFLD education; 2) diet/lifestyle support; 3) T2D medication management; and 4) clinically-indicated liver testing and care. [name] (PI) and the Clinical Research Coordinator (CRC) will deliver NAFLD education and diet/lifestyle support content. [name] (PI) will conduct medication management, which will involve review of glycemic trends, assessment of hypoglycemia and adjustment of the T2D regimen to accommodate initiation of pioglitazone, GLP-1RA and/or SGLT2i. The order in which these medications are considered will depend on clinical judgement, patient preference and cost, but GLP-1RA will be prioritized as appropriate, since this class has potent weight loss effects.¹⁶ Also, at baseline (and as indicated throughout the study), [name] (PI) will review clinical data and order clinically-indicated liver testing based on guidelines. Surveys and clinical evaluation will be repeated at study conclusion. A treatment acceptability measure (TAP)²⁰ will be administered at conclusion to gauge intervention acceptability. A detailed summary of data collection and outcome measures can be seen in Table 3.

Table 3: Detailed summary of data collection and outcomes	Method	Timing
Primary outcomes		
Feasibility		
System-level NAFLD detection	Patients who met criteria for NAFLD after chart review / total number of potentially-eligible patients based on our EHR criteria	3 months
Recruitment rate*	Patients eligible and sent letter or MyChart message / Patients enrolled	3 months
Retention rate	Patients enrolled / Patients completed study	3 months
Visit completion rate	Total study visits completed / total study visits scheduled	3 months
Acceptability		
	TAP measure ²⁰	3 months
	Qualitative interviews	3 months
Secondary outcomes of interest		
Medication changes made during the study	Study visit notes in EHR	0, 3 months
Proportion of patients in whom clinically-indicated tests were ordered (e.g. labs, referral, imaging).	Study visit notes in HER	0, 3 months
Psychosocial constructs Self-efficacy Autonomy support Quality of life	6-item SEMCD ²¹ HCCQ Diabetes ¹⁸ SF-12 ¹⁹	0,3 months
Descriptive data to characterize population		
Social and demographic Age, sex, race/ethnicity, marital status, education, employment, tobacco use, alcohol use, SDOH screen (food insecurity, housing instability, lack of transportation)	Self-reported surveys	0 months
Health literacy/numeracy	NVS	0 months
Medication adherence	VMNQ ²²	0 months
Clinical Baseline knowledge of NAFLD, years with diabetes, medical history, medication use	Self-reported surveys	0 months

Improving detection and evidence-based care of NAFLD in Latinx and Black patients with type 2 diabetes (NAFLD-DM): A pilot study

PI: [name]

Page 5 of 7

Version 2: May 31, 2024

Labs: HbA1c, AST, ALT	Use from EHR if collected within 3 months of baseline visit. Otherwise, research labs collected in DUHS at specified time points.	0 months
Biomedical Height, weight, BMI	From EHR (last recorded values)	0 months

*We will also track the number of participants who expressed interest in the study based on our recruitment flyer, and examine the recruitment rate via this approach (i.e., patients who expressed interest / patients enrolled. **Abbreviations:** TAP=Treatment Acceptability & Preferences; SDOH=social determinates of health; NAFLD=nonalcoholic fatty liver disease; BMI=body mass index; HER=electronic health record; SEMCD=Self-efficacy to Manage Chronic Disease Scale; VMNQ=Voils Medication Non-Adherence Questionnaire; NVS=Newest Vital Sign; HCCQ=Healthcare Climate Questionnaire.

Participant interviews: At study conclusion, individual 30-minute virtual interviews will be conducted with all study participants. The primary purpose will be to assess intervention acceptability and to gain specific feedback about intervention content. Thematic saturation is expected by 12 interviews.²²

Quantitative analysis: Intervention feasibility will be evaluated by examining recruitment rates, retention rates, and study visit completion rates. For the TAP measure, mean score and standard deviation will be calculated. This feasibility pilot will not be powered to examine changes in clinical measures (e.g., HbA1c, ALT).

Qualitative analysis: All interviews will be digitally recorded and transcribed. Transcripts will be analyzed with direct content analysis.²³

Improving detection and evidence-based care of NAFLD in Latinx and Black patients with type 2 diabetes (NAFLD-DM): A pilot study

PI: [name]

Page 6 of 7

Version 2: May 31, 2024

References

2. Diabetes Mellitus. *Federal Practitioner*. 2017;

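### The raised ALT that qualifies a patient may also serve as baseline, so regression to the mean can tilt the secondary pre-post ALT effect toward benefit

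*Protocol*

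**What the plan says.** - **Entry** (Protocol, Detection of NAFLD in T2D). The EHR report selects patients with a T2D code and "at least one ALT >40 IU/mL in males or > 31 IU/mL in females" within the previous 12 months. One raised value is enough. Chart review then serves to "exclude individuals with liver dysfunction likely due to an etiology other than NAFLD". Flyer respondents are screened against the same records: "We will use the EHR to determine their eligibility".
- **Baseline labs** (Protocol, baseline paragraph before Evidence-based care). If the chart holds no "ALT and ALT within 6 months of enrollment, we will order these tests to be completed at baseline". The repeated ALT is presumably a slip for AST and ALT. Table 3, Labs row, allows a chart value only within 3 months of the baseline visit, and research labs otherwise. Neither place bars the qualifying ALT or says which value to take when several fall in the window.
- **Other testing** (Protocol, Evidence-based care). At baseline the investigator "will review clinical data and order clinically-indicated liver testing based on guidelines".
- **Follow-up**. The same section says "Surveys and clinical evaluation will be repeated at study conclusion", without naming ALT. Table 3 lists ALT only among the descriptive variables, at month 0. The only test row in Table 1 is conditional: "If indicated, ordering tests and referrals".
- **Analysis** (SAP, Secondary outcomes). ALT at 12 weeks is a secondary outcome, summarised as a pre-post effect size with a 95% CI. There is no comparator and no definition of pre. The SAP's closing paragraph says the pilot should yield effect sizes for planning later work.

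**The concern.** Every participant enters because of a high ALT. If that same reading is the pre value, the comparison starts from a number chosen for being high, and the 12-week value will on average be lower whether or not the intervention works. Without a control arm nothing in the analysis separates this from a treatment effect, and the CI does not show it, because it is bias and not imprecision. A later trial planned on an inflated ALT effect would be too small. HbA1c is not an entry criterion, so this selection does not act on it directly.

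**Working it through.** **1. Figure to reproduce.** None. The documents give no ALT SD, within-person correlation, target effect or reuse share. The sample is "We will enroll 10-15 Latinx/Hispanic and 10-15 Black patients with T2D and NAFLD", so n = 20 to 30; the SAP expects 15 + 15 = 30.

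**2. Direction.** For a normally distributed (log) ALT selected above a cut-off c (in SD units), with repeat-measure correlation ρ and no true change:

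expected change = -(1 - ρ) × φ(c) / (1 - Φ(c)).

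This is negative whenever ρ < 1. With 35% of patients above the cut-off (assumed), c = 0.385 and φ(c)/0.35 = 0.370/0.35 = 1.058. With ρ = 0.8 (assumed) the change is -0.2 × 1.058 = -0.21 unselected SD. Over ρ from 0.9 to 0.5 and 50% to 20% above the cut-off it runs from -0.08 to -0.70 SD. These figures apply to a participant whose qualifying value is reused.

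**3. Share reusing the qualifying value.** Assume one raised ALT per patient, with dates uniform over the 12-month look-back.
- Enrolment on the day of the report: 3/12 = 25% (3-month window) or 6/12 = 50% (6-month window).
- Lag from report to enrolment uniform over 0-3 months (mean 1.5), report not re-run: (3 - 1.5)/12 = 12.5% or (6 - 1.5)/12 = 37.5%.

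Chart review, opt-out letter, phone call and e-consent all precede enrolment, so some lag is realistic. Several raised values per patient would push the share up; newer clinically indicated tests would push it down. The range carried forward is 12.5-50%.

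**4. Size.** Simulation with no treatment effect. Assumptions: log-normal ALT, cut-offs read as IU/L, half the participants at each cut-off, and follow-up and any fresh baseline drawn independently around the person's own mean. d = mean change / SD of change. P = share of null trials at n=30 whose 95% CI lies wholly below zero.

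| Assumed median / between-person log-SD / within-person CV | Reuse 100% (bound) | 50% | 25% | 0% |
|---|---|---|---|---|
| 28 / 0.50 / 15% | -1.72 IU/L, d -0.15, P 14% | -0.86, -0.08, 6% | -0.44, -0.04, 4% | about 0, P 2% |
| 25 / 0.45 / 20% | -3.70, -0.28, 34% | -1.86, -0.14, 12% | -0.93, -0.07, 6% | about 0, P 2% |
| 22 / 0.40 / 30% | -8.88, -0.53, 79% | -4.42, -0.25, 29% | -2.19, -0.13, 11% | about 0, P 2% |

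With the lag (12.5-37.5% reuse), d runs from -0.02 to -0.19 and P from about 3% to 18%. At n=20, P is 4-21% for 25-50% reuse. With a stable ALT (median 35, CV 10%), d is -0.02 to -0.04 at 25-50% reuse and -0.07 to -0.08 at full reuse.

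**5. Against precision.** CI half-width in SD of change = t(0.975, n-1)/√n. For n=30 this is 2.045/5.477 = 0.373; for n=20 it is 0.468. Every shift at 12.5-50% reuse is smaller than this.

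**6. Two checks on the remedy.**
- With two chart ALTs and the more recent one as baseline, dropping only participants whose recent value is above the cut-off leaves a group selected low. It shows a false rise of 4.5 to 6.3 IU/L (d +0.50 to +0.65). A fresh draw in the same people gives about 0.
- If ALT fluctuates slowly (correlation decaying over 2-6 months), even a fresh baseline leaves -0.2 to -1.5 IU/L (d -0.02 to -0.13).

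**The case against.** **The protocol already has a baseline rule.** True, and the one-page SAP should be read with it. A reader might infer that no baseline is defined anywhere; that is wrong. But the rule itself permits reuse, since a test is ordered only when no chart value falls in the window, and its two windows disagree.

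**The pilot is declared not powered for clinical measures.** Both documents say so, no feasibility or acceptability criterion depends on ALT, and an uncontrolled change cannot be read causally anyway. This limits the severity. It does not answer the point, because low power concerns precision and the SAP still wants effect sizes for planning.

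**The size is speculative.** It rests wholly on assumed ALT variability and reuse. The 29% and 79% figures come from one corner (median 22, CV 30%). A reader might infer that most of any observed ALT fall would be artefact. The documents do not support that: full reuse requires every qualifying value to lie inside the window, whereas the look-back is 12 months and older values trigger a new test.

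**Follow-up ALT may well be collected.** A reader might infer from Tables 1 and 3 that no 12-week ALT is planned. Table 1 lists visits, so a missing lab row proves little, and the protocol does repeat clinical evaluation at the end. What stands is narrower: Table 3 and the SAP disagree on whether ALT is an outcome.

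**Conclusion.** The concern holds for the secondary ALT estimate only. Following the stated rules lets the qualifying ALT act as baseline for some participants, which biases the pre-post change toward benefit. The direction needs only within-person correlation below 1. The size is an assumption-based range: d of about -0.02 to -0.25 and a false-benefit CI in about 3-29% of null trials at n=30, for 12.5-50% reuse and the three main ALT scenarios. It is always below the CI half-width of 0.37 SD and near zero if ALT is stable. Chart review for other liver disease is not modelled and may lower these figures. The primary feasibility and acceptability outcomes and their criteria are untouched. Severity is minor to moderate.

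The conflict between the 6- and 3-month windows, and the mismatch between Table 3 and the SAP on 12-week ALT, need correcting whatever the size of the bias.

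**What to change.** 1. In the SAP, define the pre ALT as a value drawn after eligibility is fixed and before the first intervention contact, wherever one exists.
2. Record the source of each baseline ALT (qualifying value, other chart value, post-eligibility draw) and report the shares. Give the ALT change for all participants, plus a sensitivity estimate restricted to post-eligibility draws. Removing only the reused values is not enough, because the remaining chart values may be selected low.
3. State in the SAP that the uncontrolled ALT change may include regression to the mean, and that some may remain even with a fresh baseline.
4. Reconcile the 6-month and 3-month ALT windows. Reconcile Table 3 with the SAP so that the 12-week ALT is listed as an outcome and collected.

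**Cost.** Wording changes and one extra field per participant; no additional baseline draws. Collecting the 12-week ALT means up to about 30 follow-up tests, which the SAP outcome already implies. Removing 25-50% reusers alone would leave 15-22 of 30 (half-width 0.55 to 0.44 SD). Dropping every in-window chart value may leave fewer. That subset is also not random: its members lacked a recent ALT or had a clinical reason for testing. Read the sensitivity estimate beside the full one, and do not make it the sole basis for planning. The reported ALT effect may look less favourable.

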Official Title: Improving Detection and Evidence-based Care of NAFLD in Latinx and Black Patients With Type 2 Diabetes (NAFLD-DM): A Pilot Study

NCT: NCT05844137

IRB Document Date: 5/31/2024

Statistical Design and Power

V: May 31,2024

We expect to enroll 15 participants who self-identify as Black or African American (AA), and 15 participants who self-identify as Hispanic/Latinx.

Our quantitative primary outcomes will be feasibility and acceptability, as below:

| | |
|---|--|
| Feasibility of system-level NAFLD detection approach | Patients who met criteria for NAFLD after chart review / total number of potentially-eligible patients based on our EHR criteria. We will deem this approach feasible if detection rates are >70%. |
| Feasibility of patient-level management | We will assess recruitment rates, retention rates and study visit completion rates. We will consider our management approach to be feasible if we can recruit at least 10 Black/AA patients and 10 Hispanic/Latinx patients over 12 weeks (3 months) |
| Acceptability of intervention by participants | We will calculate the mean and standard deviation of the Treatment Acceptability and Preferences (TAP) measure at 3 months; a score >3 will be deemed acceptable. |

Secondary outcomes: Patient-level outcomes will be examined at 12 weeks (3 months), and these include: hemoglobin A1c, alanine aminotransferase level (ALT), and survey measures (i.e., self-efficacy, perceived autonomy support and quality of life). Effect size of the pre-post difference and 95% confidence intervals will be calculated.

This pilot study will not have enough statistical power to establish effectiveness of the intervention for these secondary outcomes. Results of an intervention to improve NAFLD detection and management in Black and/or Hispanic/Latinx persons with T2D has not been previously reported. Therefore, the primary goal of this pilot study is to generate evidence in this area to estimate effect sizes and show feasibility of the intervention to guide future work.

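### The first 50 invitations are not split by group, but recruitment feasibility is judged in each group, so list order can influence the verdict

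*Protocol*

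**What the plan says.** **Invitations.** Under Research activity (Detection of NAFLD in T2D), the protocol says the DEDUCE tool "will be used to generate a report of potentially eligible Latinx and Black patients". After chart review, "The first 50 patients who meet eligibility will be mailed a letter or sent a MyChart message with opt-out instructions". No number per group, ordering rule or later batch is given.

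**Second route.** The protocol adds: "In parallel to the above recruitment approach, we will also advertise this study in the community with the help of community partners". No expected yield or group target is attached to it.

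**Targets.** These are set by group throughout. Under Study population: "We will enroll 10-15 Latinx/Hispanic and 10-15 Black patients with T2D and NAFLD". In the SAP: "We expect to enroll 15 participants who self-identify as Black or African American (AA), and 15 participants who self-identify as Hispanic/Latinx". The SAP's test for feasibility of patient-level management is whether "we can recruit at least 10 Black/AA patients and 10 Hispanic/Latinx patients over 12 weeks (3 months"). That is the only numeric threshold given for this primary outcome. Retention and visit completion are to be assessed, but without a cut-off.

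**Reporting.** Protocol Table 3 defines the recruitment rate over both groups together, as "Patients eligible and sent letter or MyChart message / Patients enrolled". The footnote covers the other route: "We will also track the number of participants who expressed interest in the study based on our recruitment flyer". Neither is planned by group.

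**The concern.** The contact rule ignores group, while the success rule applies to each group. The per-group targets show that balance is intended, but nothing in the mailing step produces it. If one group fills most of the first 50 places, the other may miss 10 simply because few of its members were invited, even when the total reaches 20 and uptake is the same in both groups. The pilot would then report patient-level management as not feasible for a reason unrelated to whether patients accept the intervention. A recruitment rate pooled over groups would not show whether the miss came from few invitations or from low uptake.

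**Working it through.** The documents state no uptake, list mix or flyer yield and contain no sample-size calculation, so there is no planned figure to reproduce. The check asks how far the chance of meeting the rule moves with the group mix at a given uptake.

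**Inputs from the documents.** 50 letters; the rule of at least 10 in each group; an expected 15 + 15 = 30 enrolled.

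**Assumptions.** Uptake per letter *p* of 40%, 50% or 60%, equal in the two groups; smaller group's share of the eligible list *s* of 50%, 40% or 30%; groups separate and independent; letters only, with one batch, unless stated.

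**Step 1: uptake needed.** If every enrollee came from the 50 letters, the minimum of 20 needs 20/50 = 40% and the SAP's expected 30 needs 30/50 = 60%. For the smaller group to reach 10 it needs 10/25 = 40% with 25 letters, 10/20 = 50% with 20, 10/15 = 67% with 15, and 10/10 = 100% with 10.

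**Step 2: fixed split.** With *a* letters to one group and 50 − *a* to the other,

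P(10+10) = P(Bin(*a*, *p*) ≥ 10) × P(Bin(50 − *a*, *p*) ≥ 10).

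At 25/25 and *p* = 50%, each factor is 0.885, and 0.885² = 0.78.

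**Step 3: unsplit list.** If the first 50 are in effect a random draw from the list, *A* ~ Bin(50, *s*), and the Step 2 probability is averaged over *A*.

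| First 50 letters | *p* = 40% | *p* = 50% | *p* = 60% |
|---|---|---|---|
| Fixed 25/25 | 33% | 78% | 97% |
| Unsplit, 50:50 list | 27% | 68% | 92% |
| Unsplit, 40:60 list | 19% | 52% | 79% |
| Unsplit, 30:70 list | 6% | 21% | 41% |
| At least 20 in total, any split | 55% | 94% | 99.9% |

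The last row does not depend on the mix. At 50% uptake the total is nearly always reached, while the per-group rule is met with probability 78% down to 21%, depending on how the letters fall.

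**Step 4: what shrinks the gap.** With *f* flyer enrollees in each group, the threshold 10 in Step 2 becomes 10 − *f*. At *f* = 3 and 50% uptake, the fixed 25/25 split gives 98.5%, against 96%, 89% and 64% for unsplit 50:50, 40:60 and 30:70 lists. At 60% uptake the figures are 99.9% against 99.5%, 97% and 82%. A second batch also helps. A 35/15 mix gives 15% at 50% uptake with one batch; doubled to 70/30, it gives 98%.

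**Step 5: unequal uptake.** If uptake is 60% in one group and 40% in the other, 25/25 gives 0.987 × 0.575 = 57%. Sending 20 letters to the first group and 30 to the second gives 72%.

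**The case against.** The strongest reply is that this is an unstated operational detail. A minimum and maximum for each group already imply that recruitment will be watched by group. More than 2,000 eligible patients are anticipated, nothing says mailing stops at 50, and the flyer runs in parallel through two community partners. A serious loss needs an uneven list, no further letters and a weak flyer yield in the smaller group, all at once. Much of this stands, and it limits the size of the point. It does not remove it: no later batch is described, and one sent without a group rule would follow the same list mix.

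Three stronger readings are tempting but not supported.

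- A reader might infer that the plan contradicts itself or that 10 + 10 is out of reach. It does not, because 50 is not called a cap and flyer enrollees count towards the rule.
- A reader might take a 35/15 split, with 15% at 50% uptake, as the expected case. The documents give no mix. From a 50:50 list, a split of 35/15 or more uneven arises in only 0.7% of random draws. The biopsy percentages in the Background (1.7% Latinx, 13% Black) describe a different population and are presented there as a disparity, so they do not estimate the mix.
- A reader might think an equal split settles the matter. Low uptake remains a main driver (33% at 40% uptake even with 25/25), and Step 5 shows that equal letters are not the best allocation when uptake differs.

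**Conclusion.** The point holds in limited form. Followed as written, the invitation rule lets list order influence a primary feasibility conclusion that the SAP draws per group. With letters alone and equal uptake, the loss against a 25/25 split is modest for a balanced list: about 10 percentage points at 50% uptake (78% to 68%) and about 5 at 60% (97% to 92%). It is large for a 30:70 list: 57 points at 50% (78% to 21%) and 56 at 60% (97% to 41%). These are illustrations under stated assumptions, not forecasts. They also assume that the top of the list behaves like a random draw; a report sorted by group could be more uneven. The change is worth making because it costs little and makes the verdict easier to interpret, not because the trial would otherwise fail.

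**What to change.** 1. In the protocol, send the first 50 invitations as 25 to Black and 25 to Latinx patients, taken in a stated order within each group.
2. State whether further letters will follow, and direct any later batch to the group still short of its target.
3. In the SAP, report enrolled/invited by group beside the 10 + 10 rule, with flyer enrollees by group shown separately. Table 3 and its footnote print these ratios the other way up and should be inverted. Enrolment per invitation is needed because later batches make 10 + 10 easier to reach.

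**Cost.** Wording in both documents and a sort of an exported list; no target or threshold changes. If charts are reviewed only as far down the list as needed, finding 25 in a group with a 30% share means reaching about 25/0.30 = 83 eligible patients rather than 50.

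**Downsides.** The sort would use race and ethnicity as recorded in the EHR, which may differ from the self-identification that the SAP counts, so a rule is needed for patients who identify with both groups. An equal split does not correct for low or unequal uptake; step 2 addresses that in part.
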